## 1. Inclusion criteria:

## Smokers:

COPD, ≥21 years old, speak and understand English, smoke on >25 of the last 30 days for the past 3 months, willing to switch from cigarettes to the study e-cigarette for the duration of the study. Have tried but failed to quit smoking in the last year, unwilling to make a pharmacotherapy-assisted quit attempt in the next 30 days,

willing to complete six in-person study visits, willing to have blood drawn, have reliable transportation to attend all in-person assessments, have a working phone number, and plan to remain in the Kansas City area for the full duration of the trial.

**Dual users:**

COPD  $\geq 21$  years old, speak and understand English, smoke on  $\geq 15$  days of the last 30 days for the past 3 months, willing to switch from cigarettes and their own e-cigarette to the study e-cigarette for the duration of the study, use an EC on  $>15$  days of the last 30 days for the past 3 months, have tried but failed to quit smoking in the last year, unwilling to make a pharmacotherapy-assisted quit attempt in the next 30 days, willing to complete six in-person study visits, willing to have blood drawn, have reliable transportation to attend all in-person assessments, have a working phone number, and plan to remain in the Kansas City area for the full duration of the trial.

2. Exclusion criteria:

**Smokers:**

Use of tobacco products other than cigarettes including e-cigarettes in the past 30 days, current use of cessation medications, pregnant, planning to become pregnant, or breastfeeding, recent history of cardiovascular or pulmonary events in the past 3 months, household member current or previously enrolled in the study, weekly use of an EC over the last 6 months

**Dual Users:**

Use of tobacco products other than cigarettes and e-cigarettes in the past 30 days, current use of cessation medications, pregnant, planning to become pregnant, or breastfeeding, recent history of cardiovascular or pulmonary events in the past 3 months, household member current or previously enrolled in the study

3. Withdrawal/Termination criteria:

Participants will be instructed to present to the lab nicotine deprived (12 hours abstinent) for the first study visit. If participants present to the first study visit with an eCO  $>12$  ppm or they report other nicotine use on two separate study visits, they will be withdrawn from the study (i.e., participants will be rescheduled one time).

4. Participants will not be allowed to participate in another research study that aims to alter their tobacco use during this research study.

**E. Specific methods and techniques used throughout the study**

1. Laboratory tests: At the beginning and end of the vaping session at Human Lab visits 1, 2, and 3 (~week 12), blood will be collected for nicotine analysis via a blood draw from the participant's arm. If deemed necessary by the study nurse (CRU staff) or by the participant, an IV catheter may be placed for blood draws. Blood sampling for changes in nicotine levels will occur at -5 minutes (pre-vaping session) and +30 minutes

(immediately post-session). No more than 7 mL of blood will be drawn per draw ( $\leq 14$  mL per visit). Blood will be processed and analyzed for nicotine and cotinine levels.

### **Human Laboratory Assessments (see Table 1 for timing):**

**Topography** will be used to objectively and passively measure EC puff patterns.

Topography is a measure of substance self-administration and has been used

successfully by our team in past trials.

Topography will be used in three ways: 1) in lab-based EC vaping sessions as an outcome variable, 2) within the intervention as outlined above, and 3) in the

natural environment throughout the RCT.

**Nicotine boost.** At all three visits, blood samples will be collected at -5 (baseline) and +30 minutes (post-session). Samples will be analyzed according to standardized methods by [name] at KUMC. Blood will be analyzed for nicotine levels to assess nicotine "boost" (i.e., change in nicotine level pre- to post-session) achieved during the EC sessions.

**eCO** will be measured at final screening and all human lab visits. A  $>50\%$  reduction in eCO from initial screening will indicate compliance with 12-hour abstinence from smoking. eCO is collected by having the participant take a deep breath in and hold it for 15 seconds and then exhaling into a straw.

**Cigarette craving/withdrawal.** The self-reported Tiffany-Drobes Questionnaire on Smoking Urges – brief (QSU-brief) and Minnesota Nicotine Withdrawal Scale (MNWS) will measure changes in cigarette craving and nicotine withdrawal from pre- to post-session.

**Other self-report assessments.** The modified self-reported Cigarette Evaluation Scale (mCES) will assess subjective effects and sensory experiences at the end of each session. Participant's intentions for future use (e.g., purchase, use) of ECs will be assessed using a 4-item measure.

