Participants will remain abstinent from nicotine/tobacco for 12 hours prior to each study visit. Abstinence will be verified by eCO (>12 ppm. Self-report will be used for EC abstinence, as there is currently no objective, reliable measure to verify non-use of these products within the time the participants will be in the lab. Participants will be provided the device of their choice with either tobacco or menthol flavored e-liquid or pods. Participants will puff ad libitum for 30 minutes to establish baseline levels. Throughout the session, puff topography will be measured. Blood sampling for changes in nicotine levels will occur at -5 minutes (pre-vaping session) and +30 minutes (immediately post-session). At the end of Human Lab Visit 1, participants will receive training on the EC based on intervention allocation. Human Lab Visit 2 will be identical to Visit 1 but will not include additional EC training. Human Lab Visit 3 (~Wk 12) will be identical to Visit 2 and will measure longer-term changes in EC puff patterns. The Evolv Reflex EC has the capacity to track and store 4 weeks of data about a participant's use of the product and puffing topography between in-person visits. eScribe topography software will be used for the device. The JUUL and Vuse devices do not collect data. Because daily use of EC is consistently one of the best predictors of exclusive EC use, we will reinforce this pattern across sessions within the enhanced EC training arm and problem-solve barriers related to daily use.

**Figure 1:** Overall study flow

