## 2. Study Procedures:

- a. **Initial Screening:** The initial screening will review inclusion/exclusion criteria by phone or online screener. Those eligible will be scheduled to complete an in-person visit within 14 days.
- b. **Final Screening (Day 0):** Participants will be instructed to smoke and vape as they normally would before the final screening. Final eligibility screening will be conducted in-person and will consist of a pregnancy test, exhaled carbon monoxide (eCO), providing evidence of EC use (bring EC to visit; dual users only), and obtaining informed consent. Participants will complete carbon monoxide (CO) measurement to confirm current smoking status (CO > 12 ppm). CO is collected by a simple, non-invasive breath test that involves the participant holding their breath for ~15 seconds and then exhaling into a straw connected to the CO monitor. Cigarette smoking will be assessed using the Timeline Followback (TLFB) in which individuals report on number of cigarettes per day (CPD) in the past 7 days. To assess baseline self-reported respiratory health, participants will complete the COPD assessment test (CAT). The modified Cigarette Evaluation Scale (mCES) will assess subjective effects and sensory experiences at the end of the session. Participant's intentions for future use (e.g., purchase, use) of ECs will be assessed using a 4-item measure. Participants will sample two e-liquid flavors (Menthol and Tobacco) to establish preference. Participants will go home with their device and e-liquid of choice to practice at home. Participants will complete baseline measures. Participants will be compensated \$10 for the final screening.

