- j. **RCT Visit – Week 12:** Participants will smoke and vape as they normally would. Participants will complete eCO measurement to confirm smoking status. Because the eCO is the only measure needed for this visit, visit location will be flexible. Visits will be conducted as determined by location and abilities of the study participant. Participants will be compensated \$10 for this visit.
- k. **Human Lab Visit 3:** Human Lab Visit 3 (Week 12) will be identical to Visit 1 (above) but will not include any training. The visit is intended to measure longer-term changes in EC puff patterns. Participants will be instructed to remain abstinent from nicotine and tobacco for 12 hours prior to the study visit. Participants will complete eCO measurement to confirm tobacco/nicotine abstinence. To assess changes in self-reported respiratory health, participants will complete the CAT. Lung function will be assessed via spirometry. Self-reported levels of cigarette craving and withdrawal will be measured using the Tiffany-Drobes QSU-brief and MNWS. The mCES will assess subjective effects and sensory experiences at the end of each session. Participant's intentions for future use (e.g., purchase, use) of ECs will be assessed using a 4-item measure. At the end of the visit, a 6-minute walk distance (6MWD) test will be done to assess the participant's overall ability to conduct everyday activities. Baseline cardiovascular functioning will be measured using Pulse Wave Velocity, a sensitive measure of arterial stiffness that shows rapid (~1 month) changes with switching to ECs. Baseline beat-to-beat blood pressure will be measured to assess blood pressure and vascular elasticity. Participants will be compensated \$50 for this visit.

- I. Monthly for 3 months post active study completion – phone follow up with participant.
3. Due to COVID-19 and the need to keep patients and researchers safe, we may use Zoom, a HIPAA compliant, university approved video conferencing software, during the visit. This will allow the participant to smoke freely (unmasked) while the researcher can watch and communicate with the participant via video conferencing from outside the clinic room. We will only enter the room when necessary and will ensure the participant is masked when research staff are present.
4. All procedures, tests, and visits are being performed solely for research purposes and are not billable to insurance.

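### At Human Lab Visit 3 the eCO abstinence check uses the pre-switch screening value, so participants who still smoke but whose usual eCO has more than halved can pass without abstaining

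*Protocol*

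**What the plan says.** Section II.E.1 (Human Laboratory Assessments) states that eCO "will be measured at final screening and all human lab visits" and that a >50% "reduction in eCO from initial screening will indicate compliance with 12-hour abstinence from smoking". Visit 3 is a human lab visit, so the rule covers it.

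The reference visit is named as initial screening, but "The initial screening will review inclusion/exclusion criteria by phone or online screener" (II.E.2.a), so no breath sample can be taken there. The usable reference is final screening (II.E.2.b), where "Participants will be instructed to smoke and vape as they normally would before the final screening" and the reading must show current smoking: "Participants will complete carbon monoxide (CO) measurement to confirm current smoking status (CO > 12 ppm".

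For Human Lab Visit 3 (II.E.2.k), participants are told to abstain from nicotine and tobacco for 12 hours, and "Participants will complete eCO measurement to confirm tobacco/nicotine abstinence". No cut-off is given there, and no step for a failed check.

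Two other places carry a 12 ppm limit. II.B applies it to each study visit, with the direction apparently reversed: "Abstinence will be verified by eCO (>12 ppm". II.D.3 attaches a consequence to readings above 12 ppm, but at the first study visit only. II.B also says that abstinence from ECs rests on self-report.

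The separate RCT Week 12 visit (II.E.2.j) takes eCO under usual behaviour: "Participants will smoke and vape as they normally would. Participants will complete eCO measurement to confirm smoking status". The protocol does not use that value as a reference for Visit 3.

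**The concern.** The rule treats a fall in eCO as evidence of recent abstinence. That is sensible at Visits 1 and 2, which come at most 14 + 5 = 19 days after final screening. By Week 12 the switching programme can itself have produced the fall, so the same reading may mean either recent abstinence or lasting reduction.

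Puff duration, craving and nicotine boost in an ad libitum session plausibly depend on how deprived the participant is. All three are taken at Visit 3, and the baseline-to-Week-12 change in puff duration is hypothesis H2c. The background section says that most smokers who take up ECs become dual users, and these reduced but continuing smokers are where false passes would arise. H2a expects the share of predominant EC users to rise with training dose. If it does, the check may be less informative in some arms than in others.

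**Working it through.** The protocol gives no figure for the accuracy of the abstinence check, so there is none to reproduce.

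**Inputs from the protocol.** Relative rule: pass if visit eCO < 0.5 × screening eCO (II.E.1). Screening eCO > 12 ppm under usual smoking (II.E.2.b). Alternative limit: 12 ppm (II.B, II.D.3), read here as a pass at 12 ppm or below.

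**Assumptions not in the protocol.** Usual eCO is proportional to the amount smoked. CO washes out exponentially with half-life h of 3 to 6 hours. Let r be the proportional cut in smoking and t the hours since the last cigarette.

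**Step 1: hours without smoking needed to pass.** The ratio of visit to screening eCO is (1 − r) × 0.5^(t/h). Setting it below 0.5 gives t > h × log2[2(1 − r)], or zero if that is negative.

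- No cut: h × 1 = 3 to 6 h
- 25% cut: h × log2(1.5) = 0.585h = 1.8 to 3.5 h
- 40% cut: h × log2(1.2) = 0.263h = 0.8 to 1.6 h
- Any cut above 50%: 0 h

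Under the same model, a full 12 hours without smoking in an unreduced smoker gives a fall of 75% (h = 6) to 94% (h = 3).

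**Step 2: single cases with no abstinence**, visit eCO = screening × (1 − r).

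| Screening eCO | Cut | Visit eCO | >50% rule | 12 ppm limit |
|---|---|---|---|---|
| 20 | 51% | 20 × 0.49 = 9.8 | pass (< 10) | pass |
| 30 | 50% | 30 × 0.50 = 15.0 | fail (not < 15) | fail |
| 30 | 60% | 30 × 0.40 = 12.0 | pass (< 15) | pass, at the limit |
| 40 | 60% | 40 × 0.40 = 16.0 | pass (< 20) | fail |

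**Step 3: allowing for day-to-day variation.** Simulated non-abstaining participants, with usual eCO lognormal (assumed median 20 ppm, log-scale SD 0.4), screening reading > 12 ppm, and a day-to-day CV of 20–40% on both readings. Share passing with no abstinence:

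| Cut in smoking | >50% rule | 12 ppm limit | Both required |
|---|---|---|---|
| 0% | 1–12% | 6–13% | 0–6% |
| 25% | 8–27% | 22–28% | 4–16% |
| 40% | 28–42% | 43% | 18–29% |
| 50% | 53–56% | 57–61% | 39–43% |
| 60% | 72–81% | 73–79% | 61–68% |
| 75% | 93–99.5% | 93–97% | 89–97% |
| 90% | about 100% | about 100% | about 100% |

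The check separates abstainers from non-abstainers reasonably well when smoking is unchanged and hardly at all after a 75% cut. Requiring both rules lowers the false-pass rate after moderate cuts but not after large ones.

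**The case against.** Several stronger readings are tempting, and the protocol does not support them.

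- **That anyone who has cut down passes.** A 25% or 40% cut shortens the abstinence needed but usually does not remove it, and a halving is about a coin flip.
- **That every predominant EC user passes falsely.** The protocol gives that term no numeric definition. Complete switchers who pass are truly abstinent from cigarettes. Their gap is vaping, which the protocol openly leaves to self-report.
- **That the problem could not be detected.** Blood is drawn 5 minutes before the session at all three lab visits and analysed for nicotine and cotinine, and craving and withdrawal are recorded before and after the session. Pre-session nicotine can show recent intake from either product. The protocol gives it no role in verifying abstinence, but the data will exist.
- **That the trained arms are biased.** All arms receive the same 12-hour instruction. Bias needs actual non-abstinence to differ by arm, which rests on H2a plus an assumption about compliance. No effect on puff duration has been quantified. Since no consequence is stated for failing at Visit 3, it is also not established that failed sessions of continuing smokers would be set aside.
- **That the main result is at risk.** The primary endpoint is the change from Visit 1 to Visit 2, 1–5 days apart.

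A simple re-reference would also be weak. From a usual Week 12 eCO of 6–8 ppm, a fall of more than half means a reading under 3–4 ppm, below the protocol's own 6 ppm threshold for a complete switch, so genuine abstainers could be flagged.

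These points limit the scope and shape the remedy. They do not remove the defect: for continuing smokers with a large reduction, the stated rule cannot tell abstinence from reduction.

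**Conclusion.** The point holds in limited form. At Human Lab Visit 3, a participant who still smokes but whose usual eCO has fallen by more than half meets the stated abstinence rule with no abstinence. Under the assumptions above, a non-abstaining participant passes in 72–81% of cases after a 60% cut and 93–99.5% after a 75% cut. With the 12 ppm limit also required, the figures are 61–68% and 89–97%. The percentages depend on the assumed proportional relation, median and day-to-day variation. The algebraic result for falls above 50% depends only on the rule and on the participant's usual eCO having fallen that far.

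Exposure is confined to the Week 12 lab outcomes: puff duration (H2c), craving and nicotine boost. A difference between arms in the quality of the check is possible if H2a is right; its direction and size are not established.

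**What to change.** 1. Reconcile II.B, II.D.3, II.E.1 and II.E.2.k into one stated Visit 3 criterion that does not rest on the screening value, and correct the reference to initial screening.
2. Hold the RCT Week 12 visit before Human Lab Visit 3, and use its usual-behaviour eCO as the reference where it is high enough for a fall to be informative.
3. Where it is not (for example near or below the protocol's 6 ppm complete-switch threshold), use self-reported time since last cigarette and last EC use, together with the pre-session nicotine level already collected, to flag sessions as not verified abstinent.
4. Report the Week 12 lab outcomes with and without flagged sessions.

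The cost is a fixed order for two Week 12 visits, a record of time since last use and one sensitivity analysis. No new blood or breath measurement is needed. The nicotine results will not be available during the visit, so that part of the flag is applied at analysis.

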### **RANDOMIZED TRIAL OF EC TRAINING**

#### **RCT Assessments (see Table 1 for timing):**

**Cigarette smoking.** Cigarette smoking will be assessed at W0, W4, W8, and W12 using the Timeline Followback (TLFB) in which individuals report on number of cigarettes per day (CPD) in the past 7 days.

**eCO** levels will be used to biochemically confirm smoking status. eCO  $<6$  ppm will indicate a complete switch.

**Respiratory health and lung function.** The COPD assessment test (CAT) is a COPD-specific 8-item questionnaire designed to assess impairment in health status of COPD patients. Participants will complete the CAT at baseline and Wks 4, 8, and 12 to assess changes in self-reported respiratory health. Lung function will be assessed via spirometry.

Measure	Table 1. Measures by timepoint					
	SCRN	V1	Human Lab	W4	W8	RCT
Topography*		X	X	X	X	X
Nicotine boost		X	X			X
eCO	X	X	X	X	X	
7-day TLFB	X	X	X	X	X	X
Health effects						
Spirometry		X				X
COPD Gold Staging	X					X
CAT	X			X	X	X
Pulse wave velocity		X				X
Beat to beat blood pressure		X				X
6MWD		X				X
Other self-report						
Cigarette craving/withdrawal		X	X			X
mCES				X		X
Subjective effects of EC		X	X			X
Behavioral intentions	X			X		X

*Notes.* Topography measured throughout 12-week switching period

**6-minute walk distance** (6MWD) will assess changes in functional activity. The 6MWD assesses an individual's overall ability to conduct everyday activities and will be conducted at baseline, W4 and W12. This measure is particularly responsive to change in smokers with COPD. Specifically, improvements in 6MWD have been found within xx weeks of smoking reduction in smokers with COPD [ref].

**Changes in cardiovascular functioning** will be measured using Pulse Wave Velocity, a sensitive measure of arterial stiffness that shows rapid (~1 month) changes with switching to ECs, at baseline and W12. In addition, we will assess changes in beat-to-beat blood pressure from baseline to W12. Beat-to-beat blood pressure is a sensitive measure of blood pressure and vascular elasticity. Measures of cardiovascular functioning will be conducted by [name] and her team. These measures are sensitive to changes in smoking and vaping status and are associated with downstream health outcomes that result from smoking, such as cardiovascular disease.

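### The only stated rule for a complete switch is eCO below 6 ppm; it is never joined to the 7-day TLFB or to any e-cigarette use.

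*Protocol*

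**What the plan says.** Under RCT Assessments, cigarette smoking is measured at Weeks 0, 4, 8 and 12 by the Timeline Followback, "in which individuals report on number of cigarettes per day (CPD) in the past 7 days". The next paragraph says that eCO "levels will be used to biochemically confirm smoking status", and then that a value below 6 "ppm will indicate a complete switch". That is the only operational definition of a complete switch in the protocol.

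Study Procedures divides Week 12 into two visits:
- **RCT Week 12 visit.** Participants smoke and vape as usual, and eCO is taken. The text adds: "Because the eCO is the only measure needed for this visit, visit location will be flexible".
- **Human Lab Visit 3.** This repeats Visit 1 without training, so it includes the TLFB. It follows an instructed 12 hours without nicotine or tobacco.

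The sample size section wants the Week 12 proportion who are predominant or complete switchers, with 15 complete cases per arm and a margin of at most 0.25. Section V.A estimates the proportion in each switch pattern and builds intervals on predominant EC users, to supply effect sizes for the later trial.

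**The concern.** A complete switch has two parts: no cigarettes, and an EC in their place. The written rule tests only the first, at one moment. A single breath reading reflects recent smoking and cannot stand in for the 7 days that the TLFB covers. It also carries no information on vaping.

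Two kinds of participant can therefore be labelled complete switchers wrongly. One still smokes lightly or intermittently and reads low on the day. The other has given up both cigarettes and the EC, which is a good result but not a switch.

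The protocol's own rationale is that benefit depends on how completely a smoker switches, and that dual users gain less than those who switch fully. A rule that can place dual users among the complete switchers blurs that distinction in the data meant to size the next trial.

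**Working it through.** **Inputs, all from the protocol**
- Complete switch: eCO below 6 ppm (RCT Assessments).
- Current smoking at final screening: CO above 12 ppm (Study Procedures, b).
- Sign of 12 hours without smoking: a more than 50% "reduction in eCO from initial screening will indicate compliance with 12-hour abstinence from smoking" (Human Laboratory Assessments).
- Dual users may enter smoking on as few as 15 of the last 30 days (inclusion criteria).
- 15 complete cases per arm, margin at most 0.25 (sample size section).

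**1. The plan's own figure.** The largest 95% margin for a proportion with n = 15 is 1.96 × √(0.5 × 0.5 / 15) = 0.253, which agrees with the stated 0.25. This margin covers sampling error only, not misclassification.

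**2. Can someone who still smokes read below 6 ppm?** The fall needed from a usual level E is (E − 6)/E, and must be slightly exceeded.

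| Usual eCO (ppm) | Reading after a 50% fall | Fall needed to reach 6 ppm |
|---|---|---|
| 12 | 6 | 50% |
| 15 | 7.5 | 60% |
| 20 | 10 | 70% |
| 30 | 15 | 80% |

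A participant who entered just above 12 ppm, with the fall that the protocol accepts after 12 hours, reads about 6 ppm. From higher starting levels that minimum fall is not enough. The exposure is therefore mainly among light or intermittent smokers. A dual user at the entry limit has up to 30 − 15 = 15 smoke-free days in 30, so a smoke-free stretch before a visit can occur without any change in smoking.

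**3. Which proportions move?**

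| True state, eCO below 6 ppm | Complete-switch proportion | Combined predominant-or-complete proportion |
|---|---|---|
| Predominant EC user who still smokes a little | rises | unchanged |
| Intermittent smoker, not a predominant EC user | rises | rises |
| Stopped both products | rises | rises |

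Each such participant adds 1/15 = 0.067, or 6.7 points, to an arm.

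**4. Illustration only.** The documents give no share f of participants who are not complete switchers but read below 6 ppm. Assume f between 0.05 and 0.30, equal across arms. The reported complete-switch proportion is p + (1 − p)f.
- For true p = 0.20: from 0.20 + 0.80 × 0.05 = 0.24 to 0.20 + 0.80 × 0.30 = 0.44.
- For a true contrast of 0.40 against 0.10: 0.30 × (1 − f), so from 0.285 down to 0.21.
- The number per arm planned from that contrast (80% power, two-sided 0.05) is n = [1.96√(2p̄(1 − p̄)) + 0.842√(p₁(1 − p₁) + p₂(1 − p₂))]² / (p₁ − p₂)², with p̄ the mean of p₁ and p₂. It is 32 for 0.10 against 0.40, 39 for 0.145 against 0.43, and 88 for 0.37 against 0.58.

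These figures show direction under the assumption. They do not estimate the bias in this trial.

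**The case against.** The strongest reply is that eCO was never meant to stand alone. The preceding sentence speaks of confirming smoking status, which presupposes a self-report, and the TLFB is described just above it and scheduled at Week 12. This is a fair reading of the intent, and it limits confidence in the point. It does not supply the rule: nothing says that reported cigarettes rule out a complete switch, or what happens when TLFB and eCO disagree.

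A reader might take the Week 12 visit sentence, "Because the eCO is the only measure needed for this visit, visit location will be flexible", as proof that eCO is the only input to the outcome. The text does not support that. The sentence concerns where the visit can be held, and the TLFB is collected at Human Lab Visit 3. Taking eCO under usual use is also a safeguard, because it prevents the 12-hour lab abstinence from producing low readings. The smoke-free half-day in the working is therefore not imposed by the trial and would have to arise on its own.

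Stopping both products may be uncommon. Participants agree to switch, are supplied with ECs, and are followed by device data on the Reflex and by pod weights at Weeks 4 and 8. No figure in the protocol settles how often it would happen. JUUL and Vuse store no data, so use of those devices is not recorded electronically.

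Finally, classification detail is often left to a SAP. Here, however, the protocol itself fixes a threshold and attaches a label to it, and that rule followed as written gives the wrong class in the cases above.

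**Conclusion.** The point stands, with moderate confidence, as an incomplete definition of a secondary outcome. The written rule can misclassify light or intermittent smokers and people who stopped both products. It affects the Week 12 switch-pattern proportions and any effect size taken from them.

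Three stronger readings are not supported:
- That every such error biases the Aim 2 switching result. Relabelling a predominant EC user as complete leaves the combined proportion where it was.
- That the inflation can be quantified. The 6.7 points are the weight of one participant, and the ranges in the working rest on an assumed f.
- That the main result is at risk. The primary endpoint is change in puff duration and does not use this rule.

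**What to change.** Define complete switch at Week 12 by three conditions together:
1. zero cigarettes on the 7-day TLFB;
2. confirmation by eCO below 6 ppm at the non-abstinent RCT Week 12 visit;
3. some EC use in the same 7 days, taken from one self-report question so that it covers every device.

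Collect the TLFB for the 7 days before that eCO reading. The Human Lab Visit 3 recall ends with instructed abstinence, and the protocol does not state the interval between the two visits. If TLFB and eCO disagree, classify the participant as not completely switched. Report those who stopped both products as their own category.

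The cost is low. TLFB and eCO are already collected, and both the recall and the EC question can be asked wherever the Week 12 visit takes place. The downside is one extra question and possibly slightly lower complete-switch rates.
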